- ¹³ Additional targeted physical exam may be performed throughout the study as needed at the Investigator's or his/her designee's discretion.
- ¹⁴ The Influenza Patient Reported Outcomes (FluPRO) Questionnaire (Appendix 14.1) must be completed (ie, self-reported) by the subject at baseline (Day 1) and daily thereafter through Day 14. Subjects who are not able to complete the questionnaire at baseline (Day 1) will be exempt from this assessment throughout the study. The FluPRO will be completed at home for subjects that are discharged from the hospital prior to Day 14.
- ¹⁵ The ordinal scale will be completed from baseline (Day 1) and daily thereafter through Day 14. For each day, subjects will be classified by the worst clinical outcome for which they qualify.
- ¹⁶ A urine or serum pregnancy test must be performed at screening locally (ie, by the investigative site) within 2 days prior to dosing. Negative results must be obtained prior to randomization.
- ¹⁷ A serum pregnancy test will be performed at the central lab for all female subjects of childbearing potential following randomization at baseline
- ¹⁸ Subjects to be enrolled based on the Investigator's discretion including any local laboratory results per SOC at institution.
- ¹⁹ See Laboratory Assessments for list of tests to be performed by the Central Lab in Appendix 14.2.
- ²⁰ Serum creatinine to be done locally within 24 hours prior to randomization, the result is required for oseltamivir dosing.
- ^{20a} ESR to be performed locally.
- ²¹ A chest x-ray or computed tomography (CT) scan taken per SOC within 72 hours before dosing is acceptable.
- ²² Healthcare utilization (total length of hospital stay, length of ICU stay, and rehospitalization) will be captured through the last follow-up visit.
- ²³ If the subject has any history of delayed gastric emptying, including premenstruation syndrome or menstruation, he or she may receive oral premedications 120 minutes prior to IV VIS410/placebo infusion.
- ²⁴ VIS410/placebo will be administered over 2 hours. Infusion time can be extended to up to 4 hours at discretion of the Investigator only if local infusion site-related symptoms occur.

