- Oxygen saturation $\geq 95\%$ on room air without support or a return to pre-infection status, if pre-infection status was $< 95\%$
- Pulse rate $\leq 100/\text{min}$
- Systolic blood pressure (SBP) ≥ 90 mm/Hg, without vasopressor use
- Respiratory rate ≤ 24 beats per minute
- Clinical status ordinal scale mean area under the curve for Days 1-7 and Days 1-14 using linear numeric scores for the ordinal categories.
- Comparison of clinical status ordinal scale scores for selected individual days (ie, Days 3, 4, 5, and 6)
- Comparison of clinical status ordinal scale scores using modified ordinal scale criteria (ie, pooling of selected severity criteria scores)
- Comparison of discrete ordinal scale parameters, including days of ventilator support, days in intensive care, and duration of hospitalization
- Number of days to resumption of normal activities
- All-cause and attributable mortality rates at Day 14, 28, and 56
- Total number of days in hospital and/or intensive care unit (ICU) from admission to discharge and rate of rehospitalization due to influenza A relapse/complication
- The incidence, severity, and duration of signs and symptoms of influenza-like illness as assessed by the FluPRO Questionnaire (see Appendix 14.1)
- Analysis of time to alleviation of signs and symptoms of influenza in the subset of subjects able to complete the Influenza Patient Reported Outcomes (FluPRO) Questionnaire at baseline and post-dose by Kaplan Meier analysis
- The percentage of subjects with new bacterial pneumonia/superinfection
- The percentage of subjects with influenza-related complications
- VIS410 population pharmacokinetic (PK) parameters in serum
- Titer of anti-VIS410 antibody positive samples
- Genotypic and/or phenotypic assessment to determine the emergence of VIS410 and oseltamivir-resistant viruses

Exploratory Endpoints

- Population PK parameters of VIS410 from nasopharyngeal secretions
- VIS410 concentration in tracheal aspirates
- The difference in viral load between VIS410 + oseltamivir and oseltamivir alone treatment groups in tracheal aspirate of subjects on mechanical ventilation
- Titer of anti-influenza A antibodies by hemagglutinin inhibition assay (HAI) in serum
- Correlations between serum and/or nasopharyngeal PK with viral load, clinical symptoms, presence of antidrug antibodies (ADAs), safety, and additional endpoints

Statistical Methods

Sample Size

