A shift from baseline table of vital sign abnormalities will be provided by assessment time point and by treatment group.

Electrocardiography

The ECG variables that will be analyzed are heart rate, PR interval, QRS interval, and QT interval. Values for QT corrected for heart rate (QTc) will be derived. QTc corrected according to Fridericia (QTcF)¹³ will be the primary correction parameter.

Actual values and changes from baseline of ECG variables will be evaluated by means of descriptive statistics by assessment time point and by treatment group.

A shift from baseline table of ECG abnormalities will be provided by assessment time point and by treatment group. For absolute QTcF interval prolongation (> 450, > 480, > 500 ms) and changes from baseline (increase > 30 and > 60 ms), a frequency table by assessment time point and by treatment group will be provided.

Signs and Symptoms of Influenza

Descriptive statistics will be used to compare the duration of symptoms of influenza-like illness by treatment group in the subset of subjects able to complete the FluPRO Questionnaire at baseline and post-dose. Frequency tabulation of the occurrence and severity of each of the subject-reported symptoms of influenza-like illness by assessment time point and by treatment group will be generated. The number and percentage of subjects who were not able to complete the assessment at each visit will be summarized.

Complications of Influenza

Complications of influenza are defined as pneumonia, myocarditis, worsening of chronic bronchitis, sinusitis, otitis or other chronic pulmonary diseases, encephalopathy, and death. Complications of influenza and use of antibiotic therapy for bacterial pneumonia will be reported by variable, treatment group, and time point. Diagnosis of bacterial pneumonia will be based on local clinical practice, usually an assessment of clinical features and any radiographic evidence of bacterial pneumonia (eg, infiltrate) and/or microbiologic evidence of bacterial pneumonia. All-cause and attributable mortality will be evaluated on Day 14 and 28.

Healthcare Resource Utilization

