Viral sensitivity to VIS410 and oseltamivir will be assessed during the study.

SCHEDULE OF ASSESSMENTS

Table 1. Schedule of Assessments

Study Time Point	Screening ¹	Day 1				Day					
		Baseline	Predose	0 Hour	End of Infusion	3	5 (± 1)	7 (± 1)	14 (± 3)	28 (± 3)	56 (± 7)
						LFU/ET Visit ²					
Screening/Administrative Assessments											
Informed consent	X										
Inclusion/exclusion criteria	X										
Medical history and demographics	X										
Nasopharyngeal swab for rapid flu test ³	X										
Onset of symptoms interview	X										
Prior medications ⁴	X	X									
Randomization ⁵		X									
Subject Diary ⁶		X									X
Safety Assessments⁷											
Supine ECG ⁸	X	X ⁹			X						
Vital signs ¹⁰	X	X ⁹	X		X	X	X	X	X	X	X
SpO ₂ ¹¹	X	X ⁹	X		X						X
Body temperature ¹²	X	X ⁹	X		X	X	X	X	X	X	X
Physical exam ¹³	X										
FluPRO Questionnaire ¹⁴		X							X		
Seven-Level ordinal scale ¹⁵		X							X		
Pregnancy test ¹⁶	X	X ¹⁷									X
Chemistry, hematology, urinalysis ^{18,19}		X					X		X	X	X
Serum creatinine ²⁰	X										
C-reactive protein (CRP)		X					X				
Erythrocyte sedimentation rate (ESR) ^{20a}		X					X		X		
Chest x-ray / CT scan ²¹	X										
Procalcitonin		X									
AEs, SAEs, and AESIs		X									X
Concomitant therapy		X									X

Study Time Point	Screening ¹	Day 1				Day					
		Baseline	Predose	0 Hour	End of Infusion	3	5 (± 1)	7 (± 1)	14 (± 3)	28 (± 3)	56 (± 7)
						LFU/ET Visit ²					
Influenza complications		X									X
VAS for assessment of resumption of normal activities		X									X
Healthcare utilization ²²		X									X
Study Agent Administration/Virologic/PK, and Immunology Assessments											
Pretreatment medications 60 minutes (± 5 min) prior to start of infusion ²³			X								
VIS410/placebo infusion ²⁴				X							
Oseltamivir therapy ²⁵				X		X					
Serum PK		X			X ²⁶		X		X	X	X
Nasopharyngeal swab ^{27,28}			X		X ²⁶	X	X	X	X	X	X
Tracheal aspirate ²⁹			X		X	X	X	X			
Serum ADA		X								X	X
Serum HAI sample		X								X	

e

¹ Screening and baseline activities may be performed on the same day.
² Subjects who terminate the study participation early are encouraged to have all follow-up safety assessments done at the time of study termination. All other subjects will return for a final follow-up visit at Day 56 ± 7 days.

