- The percentage of subjects with new bacterial pneumonia/superinfection
- The percentage of subjects with influenza-related complications
- VIS410 population pharmacokinetic (PK) parameters in serum
- Titer of anti-VIS410 antibody positive samples
- Genotypic and/or phenotypic assessment to determine the emergence of VIS410 and oseltamivir-resistant viruses

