5.2.1 Inclusion Criteria

Subjects meeting all of the following criteria are eligible to participate in this study:

1. Male and female subjects aged ≥ 18 years. For a country where the legal age of consent is >18 years old, the country requirements should be followed.
2. Test positive for influenza A by rapid antigen test or with another commercially available test on an adequate nasopharyngeal specimen in accordance with the manufacturer's instructions, or an acceptable local test including, PCR, FIA, or ELISA.
3. Onset of influenza symptoms no more than 5 days before VIS410/placebo infusion; symptoms may include cough, dyspnea, sore throat, fever, myalgias, headache, nasal symptoms (rhinorrhea, congestion), fatigue, diarrhea, anorexia, nausea, and vomiting.
4. Requirement for oxygen support including any positive pressure ventilation (PPV).
5. Women of childbearing potential must have a negative pregnancy test within 2 days prior to VIS410/placebo infusion.
6. Women should fulfill one of the following criteria:
 - a. Post-menopausal: either amenorrhea ≥ 12 months or follicle stimulating hormone > 40 mIU/mL as documented in their medical history
 - b. Surgically sterile; hysterectomy, bilateral oophorectomy, or tubal ligation
 - c. Women of childbearing potential participating in heterosexual relations must be willing to use adequate contraception from screening until 60 days post-VIS410/placebo infusion (see Section 6.2).
7. Non-vasectomized (or vasectomized less than 6 months prior to dosing) male subjects who have a female partner of childbearing potential must use an effective birth control method (see Section 6.2) when having heterosexual intercourse, from screening until 60 days post-VIS410/placebo infusion.
8. Subject is able and willing to comply with study procedures, as per protocol.
9. Subject, or a legally acceptable representative, is able to understand the purpose and risks of the study and willing to give voluntary written informed consent.

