## 4.3 Subgroups

The following subgroups may be used to provide further information on the primary efficacy endpoint and other clinical and virologic endpoints:

- Use of positive pressure ventilation
- Use of endotracheal intubation
- Time from onset of symptoms to VIS410 therapy
- Number of oseltamivir doses prior to VIS410
- Age categorization (<65 years, ≥65 years)
- Presence of underlying chronic lung disease
- Presence of coincident pneumonitis (pneumonia) at baseline
- Influenza A subtype
- Enrollment geographic region: Tiered assessments: initially, dichotomous (Northern Hemisphere and Southern Hemisphere), then with each hemisphere broken into two groups: North America (Canada and US) and Europe (Belarus, Belgium, Bulgaria, Estonia, France, Georgia, Latvia, Russia, Serbia, Spain, Ukraine and Georgia); and Asia/Oceania (Australia, Malaysia, New Zealand, Singapore, and Thailand) and South Africa. Enrollment geographic region: (northern hemisphere vs southern hemisphere)
- MITT subset comprised of subjects with positive baseline viral cultures based on TCID50
- Baseline HAI titer category (to matched virus subtype) (≤40 or >40)
- Time between onset of symptoms of influenza and treatment (< 72 hours or ≥ 72 hours)

January 17, 2019

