### **9.2.7 Complications of Influenza**

Complications of influenza are defined as pneumonia, myocarditis, worsening of chronic bronchitis, sinusitis, otitis, other chronic pulmonary diseases, encephalopathy, and death. Complications of influenza and use of antibiotic therapy for bacterial pneumonia will be reported by variable, treatment group, and time point. The number of subjects with a diagnosis of bacterial pneumonia/superinfection will be summarized by treatment group. Diagnosis of bacterial pneumonia will be based on local clinical practice, usually an assessment of clinical features and any radiographic evidence of bacterial pneumonia (e.g., infiltrate) and/or microbiologic evidence of bacterial pneumonia.

Sponsor-defined Bacterial pneumonia based on Medical History, Concomitant Medications and Adverse Events will be summarized. The definition of two Bacterial Pneumonia parameters will be based on the following criteria:

- (1) Incident Bacterial Pneumonia: defined as an adverse event of bacterial pneumonia or initiation of antibiotics Day 1 or after of greater than 2 days duration or an adverse event of pneumonia with concurrent use of antibiotics with the antibiotics initiated no more than 2 days prior to the pneumonia start date.
- (2) Any Bacterial Pneumonia: defined as Incident Bacterial Pneumonia or a medical history of bacterial pneumonia that is ongoing at time of enrollment or a medical history of pneumonia that is ongoing and being treated with antibiotics on the screening date.

All-cause and attributable mortality will be evaluated on Days 14, 28 and 56. Attributable mortality will be derived from the Complication of Influenza CRF; All-Cause mortality will be derived from Complication of Influenza, Seven-Level Ordinal Scale, Adverse Event and Study Completion CRFs.

Results of diagnostic laboratory tests (C-reactive protein (CRP), erythrocyte sedimentation rate (ESR) and procalcitonin results will be listed.

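### The influenza-complications endpoint does not require pneumonia to be new or worsened, so pneumonia present at entry can be counted and would dilute a treatment difference

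*Protocol*

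**What the plan says.** Protocol 3.2 makes "The percentage of subjects with influenza-related complications" a secondary endpoint. The list of qualifying conditions appears in the synopsis and in protocol 6.5.3 and 10.7.3: "Complications of influenza are defined as pneumonia, myocarditis, worsening of chronic bronchitis, sinusitis, otitis or other chronic pulmonary diseases, encephalopathy, and death". SAP 9.2.7 repeats it with slightly different punctuation: "Complications of influenza are defined as pneumonia, myocarditis, worsening of chronic bronchitis, sinusitis, otitis, other chronic pulmonary diseases, encephalopathy, and death". On presentation, SAP 9.2.7 says: "Complications of influenza and use of antibiotic therapy for bacterial pneumonia will be reported by variable, treatment group, and time point". The results go into Table 14.2.7.1.

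The documents treat pneumonia in four other places:

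- Protocol 3.2 has a separate secondary endpoint, "The percentage of subjects with new bacterial pneumonia/superinfection".
- Protocol 6.5.8 requires a baseline chest film or CT scan to look for pneumonia.
- SAP 4.3 lists "Presence of coincident pneumonitis (pneumonia) at baseline" among the subgroups that may be used.
- SAP 9.2.7 derives incident and any bacterial pneumonia from medical history, concomitant medication and adverse events, reported in Table 14.2.7.2. The SAP's change table explains that this was added because the complications eCRF had not been used correctly.

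Every subject must need oxygen support (protocol 5.2.1). No exclusion criterion in 5.2.2 removes patients who already have pneumonia.

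**The concern.** Treatment cannot prevent a pneumonia that was there before the infusion. If such cases enter the numerator, they add the same block of events to every arm, and they hide any new complication in the same subject, who is already a case. The observed rates move up together and the difference between arms narrows.

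This matters here because of what the trial is for. Protocol 10.1 and the synopsis say that the primary and secondary endpoints will be compared, with p-values as an indicator of sensitivity, in order to choose endpoints for Phase 3. An endpoint diluted by events that treatment cannot affect could be dropped for a reason unrelated to the drug.

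**Working it through.** **The wording.** In the list, worsening qualifies chronic bronchitis and, in the protocol's punctuation, arguably the items after it. It cannot reach pneumonia, which comes first. The neighbouring bacterial endpoint says new; this one does not. Adverse events have an onset rule (protocol 9.1.8, SAP 12.1), and complications have none. The SAP's incident/any split is confined to derived bacterial pneumonia and is not said to replace the pneumonia item in Table 14.2.7.1. Pneumonia not classed as bacterial is covered by neither. Within the incident definition, starting antibiotics on Day 1 or later for more than 2 days is enough to qualify, so an entry pneumonia first treated on Day 1 could still be classed as incident.

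**Inputs from the documents.** 40 subjects per arm (protocol 4.1; 3 × 40 = 120, which agrees with the stated total). Pooled VIS410 is 2 × 40 = 80, a comparison named in SAP 2.4.1. Tests are two-sided at 5% (SAP 4.1). No power, complication rate or baseline prevalence is stated for this endpoint, so there is no plan figure to reproduce.

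**Assumptions, not from the documents.** Baseline pneumonia share b = 30%, 50% or 70% in each arm. New-event rates are 30% on placebo and 10% on pooled VIS410.

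**Dilution.** If everyone with entry pneumonia is counted, the observed rate in an arm with new-event rate p is b + (1 − b)p. The difference between arms is therefore (1 − b)(p_placebo − p_VIS410), whatever the rates are.

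**Power.** Power = Φ[(|d| − 1.96·s0)/s1], where d is the difference in rates, s0 its standard error under the pooled rate and s1 its standard error under the separate rates.

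Worked case, b = 50%, all subjects, entry pneumonia counted:
- Rates: 0.5 + 0.5 × 0.30 = 0.65 and 0.5 + 0.5 × 0.10 = 0.55; d = 0.10.
- Pooled rate: (40 × 0.65 + 80 × 0.55)/120 = 0.583.
- s0 = √[0.583 × 0.417 × (1/40 + 1/80)] = 0.0955.
- s1 = √[0.65 × 0.35/40 + 0.55 × 0.45/80] = 0.0937.
- Power = Φ[(0.10 − 0.187)/0.0937] = 0.176.

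Same b, only subjects free of pneumonia at entry (20 v 40, rates 0.30 v 0.10):
- s0 = 0.1021, s1 = 0.1129.
- Power = Φ[(0.20 − 0.200)/0.1129] = 0.50.

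| b | Rates with entry pneumonia counted | Difference | Power, counted (40 v 80) | Subjects free at entry | Power, free at entry |
|---|---|---|---|---|---|
| 30% | 51% v 37% | 14 points | 0.311 | 28 v 56 | 0.627 |
| 50% | 65% v 55% | 10 points | 0.176 | 20 v 40 | 0.500 |
| 70% | 79% v 73% | 6 points | 0.100 | 12 v 24 | 0.345 |

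**Sensitivity to the assumed effect.** With new-event rates of 30% v 15% and no baseline pneumonia, power is 0.491 for 40 v 80 and 0.360 for 40 v 40. For 40 v 80 at b = 20% it is 0.255 with entry pneumonia counted and 0.416 in subjects free of it. At b = 60% the pair is 0.093 and 0.246. The direction is the same throughout; the size depends on b and on the assumed rates.

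**The case against.** A reader might infer that entry pneumonia definitely is scored as an outcome and swamps any treatment difference. The documents do not support either half.

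- **Whether it is scored.** Table 1 marks the "Influenza complications" row at Baseline, but the adverse-event row has the same marks, and adverse events are recorded only from dosing (protocol 6.5.1, 8.3 and 9.6). The mark therefore proves little. How entry pneumonia is handled may be settled in the eCRF or the table shells, neither of which is part of the documents.
- **Whether it swamps.** No prevalence is given. Listing baseline pneumonia as an optional subgroup shows that it was foreseen, not that it is common.

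It is also tempting to set the diluted power against 77%, the value for 30% v 10% with 40 v 80 and no baseline pneumonia. That comparison is too generous. Subjects who enter with pneumonia cannot newly develop it, so the fairer benchmark is the smaller group free of it at entry.

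Nor does chance imbalance in baseline pneumonia create false positives. Its standard deviation for 80 v 40 is √[b(1 − b)(1/80 + 1/40)], about 9 to 10 points at these values of b. Randomization makes it part of the sampling variation that a 5% test already allows for. It adds noise without raising the type I error.

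The plan also has partial safeguards: results by component and time point, the separate new bacterial pneumonia endpoint, the derived incident/any split, and the optional subgroup. The trial is declared exploratory and unpowered, and SAP 9.2.7 names no test for complications.

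All of this stands, and it limits the claim. It does not close the gap. Layout by component and time point does not say who enters the numerator, the derived split covers bacterial pneumonia only, and the subgroup is optional. An eCRF known to have been misused makes an explicit analysis rule more necessary.

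**Conclusion.** The concern holds in a limited form. As defined in both documents, the complications endpoint can count pneumonia present at entry, and doing so multiplies the risk difference by 1 − b. That factor needs no assumed event rates, only that the share b is similar across arms and that these subjects are counted. The power figures are illustrations of how well the endpoint could separate the arms. They rest on assumed values of b and of the new-event rates, and they do not describe a powered test in the plan. The loss is modest if few subjects enter with pneumonia and severe if most do, and the documents do not show which applies. This is a definition to correct before the analysis; it does not threaten the primary endpoint.

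**What to change.** In SAP 9.2.7, and in protocol 10.7.3 if it is amended, count a complication only if it starts after the start of infusion, or if one present at baseline is documented to have worsened after that point. Judge this against baseline imaging, ongoing medical history and adverse-event start dates. Use complication-form dates only if they exist: no section confirms that onset dates are recorded there, and the SAP reports that the form was misused. State which source prevails when they disagree.

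Build Table 14.2.7.1 on that rule. Report pneumonia at entry by arm as a baseline characteristic, and show the composite with and without subjects who had it. That subset is defined by a baseline feature, so the randomized comparison within it remains fair.

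The cost is SAP text, some additional derivation and programming, and a blinded review of unclear cases before database lock. The reported complication rate will be lower, and the analysis without entry-pneumonia cases will rest on fewer subjects.

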EC	ethics committee
EC ₅₀	half-maximal effective concentration
ECG	electrocardiogram
EDC	electronic data capture (system)
ELISA	enzyme-linked immunosorbent assay
ESRD	end-stage renal disease
ET	end of therapy
FDA	Food and Drug Administration
FIA	fluorescent immunoassay
FluPRO Questionnaire	Influenza Patient Reported Outcomes (FluPRO) Questionnaire
GCP	Good Clinical Practice
GI	gastrointestinal
GLP	Good Laboratory Practice
HAI	hemagglutination inhibition assay
IC ₅₀	half-maximal inhibitory concentration
ICF	Informed Consent Form
ICH	International Conference on Harmonisation
ICU	intensive care unit
IEC	independent ethics committee
IgG1	immunoglobulin G1

Abbreviation	Definition
IRB	institutional review board
ITT	intent-to-treat
IV	intravenous
IWRS	Interactive Web Response System
LFU	last follow-up
LSLV	last subject last visit
MedDRA	Medical Dictionary for Regulatory Activities
MITT	modified intent-to-treat
NOAEL	no-observed–adverse-effect level
NONMEM	software used for population pharmacokinetic modeling
NSAID	nonsteroidal anti-inflammatory drug
O ₂	oxygen
PCR	polymerase chain reaction
PK	pharmacokinetic
PO	Latin per os (by mouth)
PP	per protocol
PPV	positive pressure ventilation
PR interval	an ECG parameter
QRS interval	an ECG parameter
qRT-PCR	quantitative reverse transcriptase polymerase chain reaction
QT interval	an ECG parameter
QTc	an ECG parameter; values for QT corrected for heart rate
QTcF	QTc corrected according to Fridericia
RBC	red blood cell
RSV	respiratory syncytial virus
SAE	serious adverse event
SAP	statistical analysis plan
SBP	systolic blood pressure
SOC	standard of care
SSRE	sample size re-estimation
Study drug	VIS410 or placebo
SUSAR	suspected unexpected serious adverse reaction
TCID ₅₀	half-maximal tissue culture infective dose
TEAE	treatment-emergent adverse event
VAS	visual analog scale
VIS410	investigational product
WHO	World Health Organization

